7.2. Study and Treatment Assignment

Assignment into any of the study parts (i.e. Efficacy and Safety) and treatment subgroups (15 mg, 20 mg and placebo) will be done by the Interactive Web Response System (IWRS) system (i.e cannot be done by site staff). This assignment will take into account the modified MENQOL score, frequency and severity of hot flashes, hysterectomized vs. non-hysterectomized status, and availability of places in each study part/subgroup.

Efficacy Study part

Subjects eligible for participation in the Efficacy Study part will be randomly allocated to one of the three treatment arms [E4 15 mg (Arm 1), E4 20 mg (Arm 2) or placebo (Arm 3)] in a 1:1:1 ratio using a computer-generated randomization schedule.

Safety Study part

Subjects eligible for participation in the Safety Study part will all be allocated to treatment with E4 20 mg (Arm 4).

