7.3. Randomization

A randomization schedule will be generated within the Biometrics Department of the designated CRO by a statistician not involved in the trial. The randomization schedule will be generated by means of the PLAN procedure of SAS®. The computer program uses the method of randomly permuted blocks. The block size will not be revealed before unblinding.

An Interactive Web Response System (IWRS) will be used for the randomization procedure. A subject ready for randomization will be entered in the IWRS. The respective next subject eligible for randomization will receive the lowest available randomization number at the trial center. A randomization confirmation including treatment assignment (i.e., kit number), date and time will be sent to the center, to the designated project managers or designee of the CRO and to the Sponsor's project manager.

The randomization schedule and the complete generation procedure will be filed at a secure place by the designated CRO until the trial database is unblinded. A copy of the list will be sent to the Pharmaceutical Supply for the purpose of assigning the kits to the subjects.

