8. SUBJECT SELECTION AND DISCONTINUATION/WITHDRAWAL OF SUBJECTS

8.1. Source and Number

This will be a multicenter trial performed in multiple study sites in the United States of America and Canada. Subjects will be recruited by the investigator from his/her patients or will be recruited by recruitment campaigns. Subjects must seek treatment for the relief of menopausal symptoms, or subject may already be treated for menopausal symptoms and willing to discontinue their current treatment.

All investigators must keep a record of subjects who were considered for enrollment and were consented, but were never enrolled e.g., subject screening log to address concerns over selection bias.

This trial will enroll a total of approximately 1,000 subjects; ~600 subjects ~200 per treatment arm) in the Efficacy Study part and ~400 subjects in the Safety Study part of the trial. Enrollment will stop when the minimum required number of subjects in each study group and study part is enrolled.

The number of completers after three months of treatment in the Efficacy Study part is anticipated to be around 435, anticipating a drop-out rate of 35% and 20% for non-hysterectomized and hysterectomized women, respectively. The number of completers after 12 months of treatment is anticipated to be ~300, anticipating a drop-out rate of 50% after one year of treatment.

The number of completers in Safety Study part after 12 months of treatment is expected to be ~200, anticipating a drop-out rate of 50%.

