8.1.1. Justification of Sample Size

Efficacy Study part: based on results observed for the E4 15 mg dose in the Phase 2 study, a sample size of ~200 subjects per arm provides a power of at least 80% to simultaneously achieve a superiority (upper bound of a 95% 2-sided confidence interval [CI] lower than zero) over placebo for the four co-primary endpoints together. This sample size accounts for a dropout rate during the first 12 weeks of the study of 35% and 20% for non-hysterectomized and hysterectomized women, respectively.

It is planned to enroll approximately 100 hysterectomized and 100 non-hysterectomized subjects per treatment arm.

Safety Study part: the target number of ~400 subjects has been selected to fulfill the requirement stated in International council for harmonization of technical requirements for pharmaceuticals for human use (ICH) E1 guideline (CPMP/ICH/375/95) regarding number of subjects exposed to the drug for safety assessments.

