12.5. Analysis of Primary Efficacy Variables

All statistical tests will be supported by presenting estimates and 95% CIs for the respective treatment effects (difference to placebo). These estimates and CIs will be based on the respective statistical models used for the analysis. Since all analyses of the efficacy variables are not exploratory in nature, adjustment for multiplicity will be performed (Dunnet adjustment for the comparison of each active dose versus placebo).

The primary efficacy comparison will test the following hypotheses for each treatment arm:

- H0: The average change from baseline in the primary efficacy endpoint in the treatment arm is greater (less pronounced) or equal to the average change from baseline in the placebo arm
- H1: The average change from baseline in the primary efficacy endpoint in the treatment arm is lower (more pronounced) to the average change from baseline in the placebo arm

The two dose groups of E4 will be compared to placebo regarding the four co-primary endpoints.

A comparison between treatment arms of the change from baseline at week 1 to week 12 in the weekly frequency of moderate to severe VMS and of the change from baseline in the weekly mean severity of moderate to severe VMS will be made by using Mixed-effect Models for Repeated Measures (MMRM). The MMRM models will include treatment, week, treatment by week interaction and pooled trial centers as fixed effects and baseline as a covariate. If the pooled center effect included in the model is significant, a treatment by center interaction will be included in the model. Treatment effects will be assessed at week 4 and 12 using two separate MMRM models (one on weekly frequency and another on weekly mean severity).

The primary analysis will use the data from the ITT population. Since an MMRM model is used, missing data imputation is not necessary. Additional sensitivity analyses will be implemented in order to assess the robustness of the results. These may include sensitivity with respect to:

- An imputation of missing data (last observation carried forward [LOCF] or other)
- The modelling strategy [analysis of covariance (ANCOVA) instead of MMRM]
- Confounders (for example ethnicity, hysterectomized status)
- Populations studied (mITT, PP)
- Any combination of the above

In addition, all primary efficacy variables will be tabulated at baseline and at each post-baseline time point.

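### The primary MMRM omits hysterectomy status, which the protocol uses in assignment and ties to dropout; adding it is a near-free gain in precision and in the credibility of the missing-data assumption

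*Protocol*

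**What the plan says.** - **Model.** Protocol 12.5: "The MMRM models will include treatment, week, treatment by week interaction and pooled trial centers as fixed effects and baseline as a covariate". The Synopsis repeats these terms. There are two such models, one for weekly frequency and one for weekly mean severity. Hysterectomy status is named only later in 12.5, as an example of a confounder in a list of sensitivity analyses that the sponsor may or may not run.
- **Assignment.** Protocol 7.2, on the IWRS: "This assignment will take into account the modified MENQOL score, frequency and severity of hot flashes, hysterectomized vs. non-hysterectomized status, and availability of places". It covers both the routing to a study part and the treatment subgroup. Efficacy-part women are then allocated "in a 1:1:1 ratio using a computer-generated randomization schedule".
- **Randomization.** Protocol 7.3: "The computer program uses the method of randomly permuted blocks" and "The respective next subject eligible for randomization will receive the lowest available randomization number at the trial center". No stratification factor is named.
- **Planned mix.** Protocol 8.1.1: "It is planned to enroll approximately 100 hysterectomized and 100 non-hysterectomized subjects per treatment arm".
- **Dropout by Week 12.** Protocol 8.1: "anticipating a drop-out rate of 35% and 20% for non-hysterectomized and hysterectomized women, respectively". No dropout figure is given by arm.
- **SAP.** The supplied SAP covers the Safety Study part only. Its Introduction cites a separate Efficacy Study Part SAP v3.0 of 05Apr2022, which was not supplied.

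**The concern.** An MMRM handles dropout without bias when missingness depends only on what the model contains. Hysterectomy status is the one baseline factor for which the protocol itself gives different dropout rates, and it is not in the model.

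There is also a reason to ask whether dropout among non-hysterectomized women could differ by arm. Only these women face the bleeding and biopsy rules that can end treatment (10.4.10). Section 5.2 reports that in Phase 2, vaginal hemorrhage and endometrial thickening were seen in more subjects at E4 10 and 15 mg than in the other groups.

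Two further things are at stake. The trial is sized for at least 80% power on four co-primary endpoints jointly, so avoidable residual variance matters. And an adjustment left optional can be used or dropped once results are known.

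**Working it through.** **1. The plan's own figure.** 300 × (1 − 0.35) + 300 × (1 − 0.20) = 195 + 240 = 435 completers, which reproduces section 8.1. That is 145 per arm (65 non-hysterectomized, 80 hysterectomized). The non-hysterectomized share falls from 50% to 65/145 = 44.8%, equally in every arm if dropout depends on status alone. The 80% joint power cannot be reproduced, because no effect size, SD or correlation is given.

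**2. Yardsticks, in SD units.** The standard error (SE) of a Week 12 contrast at 145 per arm is √(2/145) = 0.117. For 80% power on one endpoint (two-sided 5%) the effect must be (1.96 + 0.842) × 0.117 = 0.33.

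**3. Chance imbalance if blocks ignore status.** Take 300 non-hysterectomized women among 600, allocated to three arms of 200.
- Variance of the count per arm = 200 × 0.5 × 0.5 × 400/599 = 33.4, so SD 5.8 and a 95% range of about 89 to 111.
- With three exchangeable arms and a fixed total, the difference between two arms has variance 3 × 33.4 = 100.2, so SD 10.0 women. On 200 that is 5.0 percentage points, with mean zero.
- By simulation, at least one arm is off 100 by more than 10 women with probability 16%, and by more than 15 with probability 2%.
- An 8-point imbalance with an assumed 0.3 SD status effect moves the estimate by 0.08 × 0.3 = 0.024 SD.

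**4. Precision.** With a status effect g (in residual SDs) and a 50/50 mix, leaving status out raises the residual variance from 1 to 1 + g²/4, so the SE is multiplied by √(1 + g²/4). For g = 0.1, 0.3 and 0.5 the factor is 1.001, 1.011 and 1.031. If status is a stratum, this is the amount by which the reported SE is too large. If it is not, it is real noise: at 200 per arm and g = 0.5, √(0.100² + (0.5 × 0.050)²) = 0.103 against 0.100, the same 3%. Pooled center may absorb part of it.

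**5. Bias at Week 12.** This is a large-sample calculation using sequential regressions at weeks 4, 8 and 12, equivalent to an MMRM with unstructured covariance under monotone dropout. Assumptions: adjacent correlation 0.7; hysterectomized dropout 20% in every arm; non-hysterectomized dropout averaging the planned 35% over two E4 arms and placebo, e.g. (2 × 45 + 15)/3 = 35. Absolute bias without status in the model, in SD:

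| Non-hysterectomized dropout, E4 / placebo | g = 0.1 | g = 0.3 | g = 0.5 |
|---|---|---|---|
| 35% / 35% | 0 | 0 | 0 |
| 40% / 25% | 0.003 | 0.010 | 0.015 |
| 45% / 15% | 0.006 | 0.018 | 0.030 |

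Zero means within Monte Carlo error (0.0003). With status in the model every cell is zero. The largest entry is 0.030/0.117 = 0.25 SE, or 0.030/0.33 = 9% of the single-endpoint effect in step 2. With more dropout on E4, the bias favors E4 if non-hysterectomized women improve less, and goes against it if they improve more.

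**6. Interaction.** With an assumed 0.2 SD treatment-by-status interaction and equal dropout by arm, the estimate shifts by 0.006 SD whether or not the status main effect is included.

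**The case against.** The strongest case on the other side has five parts.

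- **Randomization may already be stratified.** A reader might infer from 7.3 that it is not. The documents do not support that: 7.2 says status is taken into account in assigning treatment subgroups, and the Amendment 5 entry in the list of changes refers to strata (suggestive only). Silence in 7.3 makes 7.2 and 7.3 unclear together; it does not show that there is no stratum. Likewise the 100/100 split is an approximate plan, not a quota. This stands.
- **The 35%/20% figures do not imply bias.** A reader might infer that they make the Week 12 estimate biased. They are rates by status, not by arm, and equal rates across arms give zero bias in the contrast (first row of the table). Chance imbalance has mean zero and is not bias either. This stands.
- **Timing limits the mechanism.** The first scheduled on-treatment ultrasound is at Visit 4, days 85 to 91, after the Week 12 diary window of days 78 to 84. The end-of-treatment biopsy requires at least 12 weeks of treatment, and the main biopsy trigger starts after week 4. Before Week 12, what remains is mainly bleeding-related: triggered biopsies, unscheduled assessments or voluntary withdrawal. This narrows the route to bias, especially for the Week 4 endpoints, but does not close it.
- **Partly handled already.** Status is listed as a possible sensitivity covariate, and pooled center picks up some of it because Canadian sites enroll hysterectomized women only. But the sensitivity analysis is optional, and US sites have no such restriction.
- **The Efficacy SAP may include the term.** That cannot be checked here. Protocol v8.0 is dated June 21, 2022, after that SAP, and still states the model without status, so any difference would need reconciling.

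**Conclusion.** This is an improvement at almost no cost, not a flaw that invalidates the primary analysis. What the documents establish is that a factor used in assignment, planned for balance in each arm and tied to different dropout is missing from the stated primary model, and that 7.3 does not say whether it is a stratum.

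The sizes are modest. Precision lost or SE overstated is about 0.1% to 3% for assumed status effects of 0.1 to 0.5 SD. Week 12 bias is zero unless non-hysterectomized dropout differs by arm and status also predicts VMS beyond baseline and earlier weeks. When both hold, it is at most about 0.03 SD (a quarter of one SE) over the ranges tried. The status effects, dropout by arm and within-subject correlation are all assumptions, because the documents give none of them. The gain is somewhat better precision, a more credible missing-at-random assumption, and one less analytic choice left open.

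**What to change.** 1. In 12.5 and the Synopsis, add hysterectomy status and hysterectomy status by week as fixed effects in both primary MMRMs, including each version of the severity score. Do this before the data for the Visit 4 analysis are unblinded.
2. In 7.3, state whether the permuted blocks are stratified by hysterectomy status, so that it agrees with 7.2 and 8.1.1.
3. Check the Efficacy Study Part SAP v3.0 and make it and the protocol say the same.

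The cost is one baseline variable, known for every woman and already used at assignment, and the matching text edits. No patients, visits or data are added. Item 2 documents the existing scheme and does not require a new randomization list.

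The added terms do not address a treatment-by-status interaction. If consistency of effect across the two groups matters, that needs its own prespecified supportive analysis by status.

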The daily severity score as defined above will also be recomputed for post baseline weeks as $[(2 \times \text{number of moderate VMS}) + (3 \times \text{number of severe VMS})] / (\text{Total number of moderate + severe VMS})$ if at least one moderate or severe VMS is recorded during the day.

The analysis including the mild VMS will be used for submission to the FDA, the analysis without the mild VMS will be used for submission to the EMA.

Analysis of Primary Efficacy Variables:

All statistical tests will be supported by presenting estimates and 95% CIs for the respective treatment effects (difference to placebo). These estimates and CIs will be based on the respective statistical models used for the analysis. Since all analyses of the efficacy variables are not exploratory in nature, adjustment for multiplicity will be performed (Dunnet adjustment for the comparison of each active dose versus placebo).

The primary efficacy comparison will test the following hypotheses for each treatment arm:

- H0: The average change from baseline in the primary efficacy endpoint in the treatment arm is greater (less pronounced) or equal to the average change from baseline in the placebo arm
- H1: The average change from baseline in the primary efficacy endpoint in the treatment arm is lower (more pronounced) to the average change from baseline in the placebo arm

The two dose groups of E4 will be compared to placebo regarding the four co-primary efficacy endpoints.

A comparison between treatment arms of the change from baseline at week 1 to week 12 in the weekly frequency of moderate to severe VMS and of the change from baseline in the weekly mean severity of moderate to severe VMS will be made by using Mixed-effect Models for Repeated Measures (MMRM). The MMRM models will include treatment, week, treatment by week interaction, and pooled trial centers as fixed effects and baseline as a covariate. If the pooled center effect included in the model is significant, a treatment by center interaction will be included in the model. Treatment effects will be assessed at Week 4 and 12 using two separate MMRM models (one on weekly frequency and another on weekly mean severity).

The primary analysis will use the data from the ITT population. Since an MMRM model is used, missing data imputation is not necessary. Additional sensitivity analyses will be implemented in order to assess the robustness of the results. These may include sensitivity with respect to:

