7.1.3.3. Justification of E4 Dose

The objective of the Phase 2 trial with E4 was to assess the minimum effective dose of E4 for the relief of VMS. The results of this trial showed that E4 is safe and well tolerated when administered daily up to 15 mg in postmenopausal women over a period of 3 months. The effect on VMS was the most pronounced with the highest dose tested, i.e., E4 15 mg. Although this dose was associated with a significant reduction in VMS severity compared to placebo, the reduction in VMS frequency failed to reach statistical significance. The advantage over placebo was nevertheless estimated as clinically relevant given the marked placebo effect observed in this trial (65% of VMS reduction compared to baseline for the placebo group versus 84% for the E4 15 mg group). The current trial will continue to study the E4 15 mg doses as well as evaluate a higher dose (E4 20 mg) in order to further delineate the optimal E4 dose for the treatment of moderate to severe VMS.

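### The primary MMRM lists no baseline-by-week term, so one baseline slope serves Weeks 1 to 12 and the Week 12 frequency test may lose some precision

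*Protocol*

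**What the plan says.** Section 12.5 of the protocol describes "A comparison between treatment arms of the change from baseline at week 1 to week 12 in the weekly frequency of moderate to severe VMS", with mean severity handled the same way. "Treatment effects will be assessed at week 4 and 12 using two separate MMRM models", one for each outcome. The fixed effects are given as "The MMRM models will include treatment, week, treatment by week interaction and pooled trial centers as fixed effects and baseline as a covariate". The Synopsis repeats the list: "treatment by week interaction, and pooled trial centers as fixed effects and baseline as a covariate". A treatment-by-center term is added if the center effect is significant. Neither place mentions baseline-by-week, and neither states the covariance structure.

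Section 12.7 applies the same method to all VMS-related secondary variables. Among sensitivity analyses that may be done, section 12.5 names "The modelling strategy [analysis of covariance (ANCOVA) instead of MMRM".

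Section 8.1.1 states that "a sample size of ~200 subjects per arm provides a power of at least 80% to simultaneously achieve a superiority" over placebo on the four co-primary endpoints together, with superiority defined as "upper bound of a 95% 2-sided confidence interval [CI] lower than zero".

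The supplied SAP covers the Safety Study part only. Its Introduction cites an Efficacy Study Part SAP, version 3.0 of 05Apr2022, which was not supplied.

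**The concern.** The outcome is change from baseline. Its regression slope on baseline at week t equals (correlation of the week-t value with baseline) × (SD ratio) − 1. If the correlation with baseline weakens over twelve weeks at similar SDs, that slope steepens with time. It also steepens if absolute reduction builds up over the weeks and is larger in women who start higher.

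A model with one slope must then compromise. At any week where the compromise differs from the true slope, some baseline variance stays in the treatment contrast although it could have been removed.

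Weeks 4 and 12 are the only weeks tested, and success needs all four co-primary endpoints. Section 7.1.3.3 reports that the Phase 2 frequency result at 15 mg was not statistically significant, so frequency is where precision is most wanted.

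**Working it through.** **The plan's own figures.** The completer count reproduces: 300 × 0.65 + 300 × 0.80 = 195 + 240 = 435, as in section 8.1. The 80% joint power cannot be reproduced, because the documents give no effect size, SD, correlation among endpoints or weekly course.

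**Formula.** Let b_t be the true slope at week t, b* the common slope the model settles on, Var(B) the baseline variance and Σ_tt the residual variance at week t. With complete data and an unstructured covariance Σ:

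- b* = (1′Σ⁻¹b) / (1′Σ⁻¹1)
- variance inflation (VIF) at week t = 1 + (b_t − b*)² × Var(B) / Σ_tt
- power = Φ((1.960 + z_power)/√VIF − 1.960), at 5% two-sided and ignoring the Dunnett adjustment

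All inputs below are assumptions; the documents supply none of them.

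**A. Reduction fully proportional to baseline, residual SD constant.** Baseline SD 25 and residual SD 25 per week; mean reduction 77.7% by Week 12, approached with a time constant of 2.5 weeks. Slopes are −0.26, −0.63 and −0.78 at Weeks 1, 4 and 12.
- AR(1) 0.9: b* = −0.571. Week 12 VIF = 1 + (0.777 − 0.571)² × 625/625 = 1.042. Week 4 VIF = 1.003.
- AR(1) 0.8: 1.032 at Week 12. Compound symmetry 0.7: 1.016.
- With half the proportionality, Week 12 VIF is 1.004 to 1.011.

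**B. As A, fully proportional, but residual SD grows from 70% to 100% of its Week 12 value.** The early weeks pull b* towards them. Week 12 VIF is 1.07 (AR 0.8), 1.11 (AR 0.9) and 1.25 (compound symmetry 0.7, where b* = −0.275).

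**C. No proportionality; correlation with baseline simply decays.** SD 25 at every week, AR(1) including baseline. At 0.90 the Week 12 slope is 0.9¹² − 1 = −0.718, b* = −0.189, and the residual variance is 625 × (1 − 0.9²⁴) = 575. VIF = 1 + 0.529² × 625/575 = 1.30. Across AR(1) values of 0.80 to 0.97, Week 12 VIF is 1.14 to 1.30 and Week 4 is 1.03 to 1.04. Giving 30–70% of the variance to a stable subject component lowers Week 12 to about 1.05–1.20. A further 10% of week-to-week noise lowers it to about 1.02–1.11.

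**D. Proportional reduction that varies between women.** Baseline mean 75, SD 25; mean reduction 72%, SD 0.2–0.3; time constant 1.5–4 weeks. Week 12 VIF is 1.24–1.55 and Week 4 is 1.22–1.34. These figures are sensitive to the week-to-week noise assumed.

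**Wider grid.** Over 648 combinations of baseline SD, residual SD, slope, time course and correlation, Week 12 VIF has median 1.014, 95th percentile 1.19 and maximum 2.29. Week 4 has median 1.003, 95th percentile 1.11 and maximum 1.76.

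**Simulation.** Four scenarios were run with 200 trials each and 200 women per arm, three of them with dropout. The variance ratio (planned over extended model) was 0.99–1.03 at Week 4 and 1.00–1.13 at Week 12, with Monte Carlo error of several percent. The mean Week 12 effect was essentially the same under both models, for example −9.82 and −9.84 against a true −10.

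**Severity.** Assume baseline SD 0.2–0.4, residual SD 0.6–0.8 and a slope gap of 0.1–0.5. The worst case is 1 + 0.5² × 0.4²/0.6² = 1.11; most cases lie below 1.04.

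**Power for a single test.**

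| VIF | from 80% | from 94.6% |
|---|---|---|
| 1.01 | 79.6% | 94.4% |
| 1.04 | 78.4% | 93.8% |
| 1.10 | 76.2% | 92.5% |
| 1.20 | 72.5% | 90.3% |
| 1.30 | 69.0% | 87.9% |
| 1.50 | 62.8% | 83.0% |

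The second column starts from 0.80^(1/4) = 0.946, the power each endpoint would need if the four were independent.

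**The case against.** The case against rests on four points.

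- **The premise is not documented.** The only relevant figure is "65% of VMS reduction compared to baseline for the placebo group versus 84% for the E4 15 mg group". It is a group percentage with no week, SD or link to a woman's own baseline. A reader might infer from it that individual reduction is proportional to baseline and grows over the weeks; the documents do not show this. The objection stands, although case C shows that slopes can diverge without proportionality.
- **The common slope need not sit near Week 1.** With constant residual SD it falls near the Week 4 slope, Week 4 loses almost nothing and Week 12 loses little. This stands for that variance pattern. However, a residual SD that grows from Week 1 is also plausible, since Week 1 lies closest to baseline.
- **Severity has little baseline variance to remove.** On any baseline day with a moderate or severe VMS the daily score lies between 2 and 3. This stands, so a loss on all four co-primary tests should not be claimed.
- **The governing text may differ.** The Efficacy Study Part SAP may include the term, and the ANCOVA sensitivity analysis, fitted at one week, would free the slope. Both stand, but the ANCOVA is optional and is not the primary test.

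Sensitivity of the estimate to chance baseline imbalance might look like a further harm. It is the same variance loss seen from another side, because randomization keeps the contrast unbiased over repeated trials.

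**Conclusion.** The listed model constrains the baseline slope to be equal over Weeks 1 to 12, and nothing in the supplied documents justifies that constraint. If slopes differ by week, Week 12 frequency may lose precision, Week 4 usually less, and severity probably little.

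Under the assumed inputs, Week 12 inflation is about 1.00–1.04 with constant residual SD, roughly 1.1–1.3 where residual SD grows or correlation with baseline decays, and about 1.5 towards the upper end. The 2.29 grid maximum is an isolated extreme.

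A reader might infer that power is certainly and substantially lost. The documents do not support that: the size depends on variances they do not give, and the plan's 80% is joint across four endpoints, so no shortfall can be demonstrated. This is an inexpensive gain in efficiency, not a flaw in validity. Confidence is high on the structure of the listed model and moderate on the size of the effect.

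**What to change.** In section 12.5 and the Synopsis, list the fixed effects as treatment, week, treatment-by-week, pooled center, baseline and baseline-by-week. Use the same list for the frequency and severity models and for the VMS secondary models that follow them under section 12.7. State the covariance structure in the same place.

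If Efficacy Study Part SAP version 3.0 already contains the term, only the protocol wording needs aligning. Make the change before unblinding, since the term cannot credibly be added afterwards.

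The cost is 11 extra fixed-effect parameters per model (12 weeks − 1) with about 600 women, one line of text and no new data.
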